Study Objective and Specific Aims	
The primary objective of this study is to evaluate safety and tolerability of the study product in adult and pediatric participants with PKAN.
 
The primary aims are:
 
• To compare safety or tolerability profiles of the study product between active and placebo groups over the 6-month double-blind parallel group phase of the study; and• To examine the long-term safety and tolerability profile of the compound over the 18-month (placebo group) -24-month (active group) active treatment period 
The primary hypothesis is that there will be no clinically significant difference in safety or tolerability profiles between active and placebo groups during six months of double-blind parallel study, nor between initial dose groups over 18-24 months of treatment with the study product.
 
The secondary aim is:
 
To evaluate the peripheral pharmacodynamic response of one component of a PKAN "molecular signature" (CoASY mRNA expression levels) in response to the study product.
 
The secondary hypotheses are that:
 
• CoASY mRNA expression levels will initially rise in all the study product-treated participants after 3 days ±2 days of treatment compared with placebo-treated participants; and• CoASY mRNA expression levels will subsequently decline in all participants after up to 18 months of study product treatment, consistent with secondary down-regulation of CoASY activity in the presence of excess substrate, (i.e. feedback inhibition); and

eIRB 18782 CoA-Z in PKAN (NIH)

	
There will be no difference in CoASY mRNA expression between initial treatment groups after up to 18 months of the single-dose active study product treatment. 
In a third exploratory aim, with the goal of informing future studies of the study product or other putative disease-modifying therapeutics, we will assess the feasibility of applying a latent growth curve (LGC) approach to natural history data collected before and during an intervention to detect disease-modifying effects.

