Sample Size Considerations	
Because PKAN is an ultra-rare disease, we are limited to 64 participants for the Primary Cohort (15 in each arm + 4 potential dropouts allowing for 5% loss to follow-up) whom we will recruit from our established research registry, (prioritizing those participating in our “PKANready” ongoing natural history study) as well as by methods described within the protocol. When our double-blind enrollment goal is met, enrollment of up to 86 additional participants will shift to an open-label arm, designated the Open-label Cohort. Our primary objective is to estimate effects of the study product and we will prioritize effect sizes over statistical power in interpreting results. Still, we wish to include sufficient numbers to estimate effects in our secondary and exploratory analyses of CoASY mRNA expression levels with some precision. In preliminary cross-sectional data, we found that the mean CoASY delta Ct (dCt) measures were 1.4 standard deviations higher in classic PKAN children (n=8) than age-matched healthy controls (n=6) on the log₂ scale, where higher dCt indicates lower CoASY activity (mean=17.39 vs 16.85, SD=0.39). We anticipate that participants at all three dose levels will resemble healthy controls after 3±2 days, while the placebo group will show no change. We simulated this change from baseline for 12 participants per group. For the standard deviation, we performed one set of simulations using the upper limit of the 60% CI for the standard deviation (0.34-0.48) as a conservative estimate. We regressed the dCt value on four indicator variables for study arm after treatment, with the intercept representing the common mean baseline value, and included a random intercept to induce correlation between paired measurements. We then used a Wald test for $\beta_{\text{placebo}1} - (\beta_{\text{low}1} + \beta_{\text{mid}1} + \beta_{\text{high}1})/3 = 0$ at $\alpha=0.05$. Pooling over 1000 simulated datasets, we find that we reject the null in 85-95% of simulations, approximating power to detect this difference at one month between the active and placebo groups.

-----------------------------------	---

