The secondary objective of this study is to assess the pharmacodynamic profile of an exploratory, 'proof-of-concept' molecular biomarker (CoASY mRNA expression) in response to the study product.

3. The secondary hypothesis is that CoASY is an inducible enzyme that will respond rapidly to exogenous substrate (4'-PPT) and subsequently decline in activity as a result of excess substrate and feedback inhibition; and that these changes will be detectable in peripheral CoASY mRNA expression levels. We anticipate that:

- CoASY mRNA expression levels will initially rise in all 4'-PPT-treated participants after 3 days ±2 days of treatment compared with placebo-treated participants; and
- CoASY mRNA expression levels will subsequently decline in all participants after completing treatment with 4'-PPT treatment, consistent with secondary down-regulation of CoASY activity in the presence of excess substrate, (i.e. feedback inhibition) and there will be no difference in CoASY mRNA expression between groups at 18-24 months.

The secondary endpoint is CoASY mRNA expression levels measured at 8 time points in the Primary Cohort and up to 6 timepoints in the Open-label Cohort.

In addition, in a third exploratory aim, with the goal of informing future studies of 4'-PPT or other compounds, we will assess the feasibility of applying a latent growth curve (LGC) approach to natural

history data collected before and during an intervention to capture a disease-modifying effect. The natural history data is being collected under a separate IRB-approved protocol eIRB 10832.

4. Background

a. PKAN is an ultra-rare inborn error of metabolism that disproportionately affects children and causes severe disability

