This will be a single site, phase 2, safety and tolerability trial of 4'-phosphopantetheine (4'-PPT), a downstream product of intermediary metabolism in children and adults with PKAN, a inborn error of vitamin B5 metabolism. An initial 6-month, dose-ranging, parallel-group, randomized, double-blind, placebo-controlled phase will be followed by an 18-month, single-dose, open-label phase. There will be up to 2 months for screening and up to 2 months for follow up for up to a total of 28 months participation for this Primary Cohort. During the double-blind phase, participants in the Primary Cohort will be assigned randomly to one of three dose groups or placebo, with a 1:1:1:1 distribution. Once we meet our enrollment target for the Primary Cohort, we will shift additional enrollment directly into a single-dose open-label arm that will last up to 18 months per participant including up to 2 months for screening and up to 2 months for follow up. Our primary hypothesis is that there will be no clinically significant difference in safety or tolerability profiles between active and placebo groups during six months of double-blind parallel-group study, nor between dose groups over up to 18 months of treatment with 4'-PPT. Safety measures will include treatment-emergent adverse events collected at 10 time points and abnormalities on standard laboratory tests collected at 9 time points over 25 months (including follow up) for Primary Cohort participants. For the Open-label Cohort, treatment-emergent adverse events will be collected at up to 7 time points and safety labs at up to 6 time points over up to 20 months (including follow up). Participants will be stratified by PKAN type: classic or atypical, to ensure approximately equal distribution in each arm.

As a secondary, “proof of concept” aim, we will assess the pharmacodynamic profile of CoASY mRNA expression in the peripheral blood of participants receiving 4'-PPT or placebo. We will measure CoASY mRNA expression at 8 time points for the Primary Cohort and at up to 6 timepoints for the Open-label Cohort to examine four secondary hypotheses:

- a. **CoASY mRNA expression levels will rise in all 4'-PPT-treated participants after 1 month of treatment** compared with placebo-treated participants.

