- b. There will be **no difference in CoASY mRNA expression between 4'-PPT dose groups after 1 month of treatment**. Statistical tests will fail to reject the null and the magnitude of the difference will be small compared to the one-month change.
- c. **After 6 months of treatment, CoASY mRNA expression levels will vary inversely with 4'-PPT dose**, and
- d. There will be **no difference between initial dose groups [placebo/active] after up to 18 months on the same active dose**, consistent with down-regulation of CoASY activity in the presence of excess substrate, (i.e. feedback inhibition).

6. Study Product

The study product is 4'-phosphopantetheine (4'-PPT) formulated in a fruit-flavored syrup suitable for administration by mouth or via G-tube. Several factors contribute to the prediction that 4'-PPT is of very low toxic potential^[9]. First, it is a synthetic version of a naturally-occurring product of intermediary metabolism in the vitamin B5 pathway [See Figure 1]. Second, the compound has shown no evidence of toxicity when given to mice in doses far in excess of those used in this trial. Third and perhaps most important, it will be used in very low doses intended to mimic physiologic levels: all doses employed in the study are based on a range tested in the mouse model as the ‘minimum effective’, rather than the more usual ‘maximum tolerated’ doses. Although derived from mouse studies, the dose range to be used in this trial turns out to be remarkably close to the molar equivalent of the Recommended Daily Allowance (RDA) of pantothenate, the upstream vitamin the study product aims to replace, which itself shows little toxicity even in doses far in excess of the RDA, with no upper limit established by the Institute of Medicine^[10].

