Because PKAN is an ultra-rare disease, we are limited to 64 participants (15 in each arm + 4 potential dropouts allowing for 5% loss to follow-up) whom we will recruit from our established research registry, (prioritizing those participating in our "PKANready" ongoing natural history study) as well as by methods described within the protocol. This will be designated the "Primary Cohort". When our double-blind enrollment goal is met, enrollment of up to 86 additional participants will shift to an open-label arm; this will be designated the "Open-label Cohort". Enrollment into this cohort will be rolling, and thus the duration of follow up will vary based on the point of entry in the overall life of the

study. Our primary objective is to estimate effects of the study product and we will prioritize effect sizes over statistical power in interpreting results. Still, we wish to include sufficient numbers to estimate effects in our secondary and exploratory analyses of CoASY mRNA expression levels with some precision. In preliminary cross-sectional data, we found that the mean CoASY delta Ct (dCt) measures were 1.4 standard deviations higher in classic PKAN children (n=8) than age-matched healthy controls (n=6) on the \log_2 scale, where higher dCt indicates lower CoASY activity (mean=17.39 vs 16.85, SD=0.39). We anticipate that participants at all three dose levels will resemble healthy controls after 3 ± 2 days, while the placebo group will show no change. We simulated this change from baseline for 12 participants per group. For the standard deviation, we performed one set of simulations using the upper limit of the 60% CI for the standard deviation (0.34-0.48) as a conservative estimate. We regressed the dCt value on four indicator variables for study arm after treatment, with the intercept representing the common mean baseline value, and included a random intercept to induce correlation between paired measurements. We then used a Wald test for $\beta_{\text{placebo1}} - (\beta_{\text{low1}} + \beta_{\text{mid1}} + \beta_{\text{high1}})/3 = 0$ at $\alpha=0.05$. Pooling over 1000 simulated datasets, we find that we reject the null in 85-95% of simulations, approximating power to detect this difference at one month between the active and placebo groups.

b. Statistical plan for primary and secondary aims

Safety Analysis

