We will compare the number of participants retained in each arm at each of the follow-up time points [0-(0+1week)-1-3-6-(6M+1week)-7-9-12-18-24-25 months for the Primary Cohort; and 0-(0+1week) -1-3-6-9-12-18-19 for the Open-label Cohort], taking into account whether dropout seems plausibly related to study participation and the mean percent of study product consumed. High retention in the study and product consumption per-protocol will be considered evidence of tolerability.

Analysis of secondary endpoints

We will estimate a CoASY pharmacodynamic profile in response to different doses of the study product in the Per-Protocol dataset. CoASY mRNA expression levels are continuous, measured in normalized differences in cycle times (ΔCt) on the \log_2 scale. Lower ΔCt indicates higher expression levels. We will use regression models controlling for PKAN type to estimate mean levels by treatment arms, including mixed effects when modeling over multiple time points.

To estimate the **change in expression levels after 3±2 days of treatment compared to placebo**, we will use a mixed effects regression model of the form $CoASY_{ijt} = \beta_0 + \beta_{jt}I(group = j)I(time = t \text{ and } t > 0) + \alpha I(cPKAN) + b_i$, $j = \text{placebo, low, mid, high}$; $t = 1$. Each individual contributes two observations (baseline and after); b_i represents the random intercept for subject. Baseline, represented by β_0 , is constrained to be the same for all groups because of randomization. Our primary approach will treat time as binary (0=baseline, 1=treated), though this can later be expanded to capture differences between days 1-5 of treatment. The β_{jt} represent mean changes from baseline for the three dose groups and placebo. An indicator for PKAN type (cPKAN or aPKAN) is included to reflect its role in stratified randomization. We will review regression coefficients as estimates of the magnitude of effect and test $\beta_{\text{placebo}1} - (\beta_{\text{low}1} + \beta_{\text{mid}1} + \beta_{\text{high}1})/3 = 0$ with a two-sided alpha of 0.1 to determine whether CoASY mRNA expression levels rose in all the study product-treated participants after initiation of treatment compared to placebo.

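### The first CoASY hypotheses and the power claim are set at 1 month, but the aims, the simulated change and the only initiation contrast are at 3±2 days

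*Combined protocol and SAP*

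**What the plan says.** **At 1 month.** Section 5 (Study Design) lists four secondary hypotheses. Hypothesis a is that "CoASY mRNA expression levels will rise in all 4'-PPT-treated participants after 1 month of treatment", against placebo. Hypothesis b is that there will be "no difference in CoASY mRNA expression between 4'-PPT dose groups after 1 month of treatment", with the criterion that "Statistical tests will fail to reject the null and the magnitude of the difference will be small compared to the one-month change". The sample size text (synopsis, Sample Size Considerations; protocol Section 10.a) closes by describing its result as "approximating power to detect this difference at one month between the active and placebo groups".

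**At 3±2 days.** The synopsis aims say that CoASY expression "will initially rise in all the study product-treated participants after 3 days ±2 days of treatment". The secondary hypothesis in the protocol body (Section 3) agrees: "CoASY mRNA expression levels will initially rise in all 4'-PPT-treated participants after 3 days ±2 days of treatment". Neither list contains hypothesis b. The sample size text assumes that treated participants will "resemble healthy controls after 3±2 days, while the placebo group will show no change". The analysis of secondary endpoints (synopsis, Statistical Methods; Section 10.b) fits a mixed model with a baseline and one post-treatment observation per person, time coded as binary. It tests placebo against the mean of the three dose groups at two-sided alpha 0.1.

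**Month 1 data.** The Primary Cohort schedule of activities marks biomarker labs at Visit 2 (Month 1).

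**The concern.** A formal secondary test has two stated time points. The trial expects CoASY expression to rise and later to decline, so 3±2 days and Month 1 may lie at different places on the curve and give different answers. If they do, the documents would support calling either result the test of the lead biomarker hypothesis. The reader of the power paragraph is also told that the trial is powered at a time that was not simulated. Hypothesis b is the less well specified of the two: it has no named contrast, no definition of a small difference and no power, and it takes failure to reject as part of its support.

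**Working it through.** **1. Time points side by side**

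| Place | Time of the initial rise |
|---|---|
| Synopsis, aims | 3±2 days |
| Protocol body, Section 3 | 3±2 days |
| Section 5, hypotheses a and b | 1 month |
| Sample size text, assumed change | 3±2 days |
| Sample size text, power conclusion | 1 month |
| Analysis model, initiation contrast | 3±2 days |

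The analysis section names contrasts for 3±2 days, for the placebo group's start of treatment after month 6, and for six months. A longitudinal model over 24 months follows. None of these is a Month 1 contrast or a comparison among doses at Month 1.

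**2. Reproducing the 85-95%**

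Inputs from the sample size text: means 17.39 and 16.85, so the effect is 0.54 dCt; SD 0.39, so 0.54/0.39 = 1.38 SD (stated as 1.4); conservative SD 0.48; 12 per group, so 12 placebo against 36 active; alpha 0.05. The random-intercept SD is not given. It is assumed here to be 0.30, a value chosen because it matches the stated range.

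With a common baseline and two observations per person, let V be the total variance (residual variance plus intercept variance) and ρ the intercept variance divided by V. Then

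SE² = V(1 − ρ²)(1/12 + 1/36), and power ≈ Φ(0.54/SE − 1.96).

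- Residual SD 0.39: V = 0.1521 + 0.0900 = 0.2421; ρ = 0.372; SE = √(0.2086 × 0.1111) = 0.152; power = Φ(3.55 − 1.96) = 94%.
- Residual SD 0.48: V = 0.2304 + 0.0900 = 0.3204; ρ = 0.281; SE = √(0.2951 × 0.1111) = 0.181; power = Φ(2.98 − 1.96) = 85%.

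Other assumptions move the range. An intercept SD of 0.20 gives 97% and 88%, and 0.39 gives 92% and 82%. Reading 0.39 and 0.48 as total SDs with no correlation gives 99% and 92%. The stated figure is therefore reachable from the stated inputs.

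**3. What the figure says about Month 1**

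Time is not a parameter of the calculation. The result applies at any visit where the mean difference is 0.54 dCt, and the documents assume that difference only at 3±2 days. They give no Month 1 effect, so the retained fraction below is an assumption (alpha 0.05; each range runs from SD 0.48 to SD 0.39).

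| Effect retained at Month 1 | Intercept SD 0.30 | Total SD, no correlation |
|---|---|---|
| 100% (0.54) | 85-94% | 92-99% |
| 75% (0.405) | 61-76% | 72-88% |
| 50% (0.27) | 32-43% | 39-55% |

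**The case against.** The best defence is that the statistical section is consistent. Synopsis and body name the same initiation contrast at 3±2 days, and the aims and the simulated change agree with it. The outliers are two hypotheses in Section 5 and one clause on power. CoASY is a secondary, proof-of-concept biomarker; the sample size is set by rarity; effect sizes are prioritised over power; and a p-value below 0.1 counts only if magnitude and precision support it. The primary safety and tolerability analyses are untouched. All of this stands, and it limits the weight of the point. It does not remove the conflict, because a formal test is still specified and two of the four Section 5 hypotheses have no named test at their stated time.

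Four stronger readings are tempting, and the documents do not support them.

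- *That the model cannot test hypothesis b.* It has a separate coefficient for each arm, so equality of low, mid and high is a contrast of existing parameters once a Month 1 term is added. The synopsis allows later extension to further time points, and Month 1 samples could enter the 24-month model. Both routes are optional or exploratory, and neither defines a Month 1 test.
- *That the two times will give opposite answers.* No text predicts a fall by Month 1. Some decrease is expected at six months, and hypothesis a itself predicts a rise at one month.
- *That false positives reach 19%.* 1 − 0.9² = 0.19 is a two-sided upper bound for two independent looks. These looks share participants, baseline and placebo group. For a false claim of a rise specifically, the bound under independence is 1 − 0.95² = 9.75%.
- *That the 85-95% is wrong.* Only its time label is.

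**Conclusion.** The contradiction is real and appears in the current text, with the power clause repeated in synopsis and protocol body. Hypotheses a and b are stated at a time for which no contrast is named, and power is claimed for a time that was not simulated. Relabelling leaves 85-95% unchanged. Reading it as Month 1 power requires the unstated assumption that the whole 0.54 dCt effect persists; with half retained, power would be about 32-55% across the two variance readings tabulated. Those figures rest on assumed retention and on assumptions about the variance structure, so they show sensitivity and do not predict the Month 1 result. This should be corrected, but it does not threaten the primary objective.

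**What to change.** Before unblinding:

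1. Name one time point as the test of hypothesis a and use it in the synopsis aims, the protocol's secondary hypothesis, Section 5, both sample size texts and both analysis sections. Choosing 3±2 days needs the fewest edits, because the aims, simulation and model already use it.
2. Change the power clause to refer to 3±2 days. The figure stays as it is.
3. For hypothesis b, either move it to the same time point, or add a Month 1 term to the same mixed model with a labelled secondary active-versus-placebo contrast and low, mid and high contrasts. In either case report the dose differences as estimates with confidence intervals, and do not judge them by non-rejection alone.

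The cost is wording and, under the second option, a little extra analysis and one more labelled secondary active-versus-placebo contrast alongside the dose estimates. The Month 1 samples are already scheduled.

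### No margin or confidence-interval rule defines 'no difference' between CoASY groups: hypothesis b relies on non-rejection plus an unquantified 'small' difference, and hypothesis d states no criterion

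*Combined protocol and SAP*

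**What the plan says.** Section 5 (Study Design) lists four secondary hypotheses for CoASY mRNA expression. Two are equality claims.

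- **Hypothesis b** predicts that the three dose groups do not differ after 1 month, and says what will show it: "Statistical tests will fail to reject the null and the magnitude of the difference will be small compared to the one-month change". This has two parts, non-rejection and a small observed difference.
- **Hypothesis d** predicts "no difference between initial dose groups [placebo/active] after up to 18 months on the same active dose", and reads this as consistent with feedback inhibition. The synopsis (Study Objective and Specific Aims) has the same prediction: "no difference in CoASY mRNA expression between initial treatment groups". Neither place gives a test, a magnitude condition or a margin.

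The analysis text (synopsis, Statistical Methods; section 10b) specifies a placebo versus mean-active contrast at two-sided alpha 0.1, an ordering of the arms at six months, and a longitudinal group-by-time model. It names no comparison for dose equality at 1 month. The stated simulated power of 85-95% (section 10a) applies only to placebo versus the mean of the three active arms.

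**The concern.** A non-significant test in small arms is weak evidence that the arms are equal. The second part of hypothesis b, "the magnitude of the difference will be small compared to the one-month change", could supply what is missing, but it concerns the point estimate, has no cut-off and is not tied to the estimate's precision. Someone reading the results would have to decide what counts as small after seeing them. For hypothesis d there is nothing to apply at all.

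The synopsis says that the range of doses is used only to test the pharmacodynamic hypotheses, so the dose comparison is part of the reason for having three active arms. What is at stake is whether the report can say that the doses, or the initial groups, behaved alike.

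**Working it through.** **Inputs from the documents.** Means and SD: "mean=17.39 vs 16.85, SD=0.39", so the assumed effect is 17.39 - 16.85 = 0.54 dCt, and half of it is 0.27. Upper SD 0.48: "the upper limit of the 60% CI for the standard deviation (0.34-0.48) as a conservative estimate". Simulation size: "We simulated this change from baseline for 12 participants per group". Planned evaluable size: 15 per arm. Alpha: 0.1 two-sided.

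**Assumptions.** The correlation between paired measurements is not given; the plan says only that it "included a random intercept to induce correlation between paired measurements". It is also not stated whether the SD is total or residual. Both readings are shown. Alpha 0.1 is taken to apply to a dose comparison, and 0.54 is taken as the one-month change. All results are for one pair of arms, by normal approximation.

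**The plan's own figure.** For placebo versus mean active with 12 per group, alpha 0.05 and the SD read as residual:

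SE = SD x sqrt(1 + ICC) x sqrt(1/12 + 1/36)

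At ICC 0.27 this is 0.1465 (SD 0.39) or 0.1803 (SD 0.48). Power = Phi(0.54/SE - 1.96) = 95.8% or 85.0%, which matches the stated 85-95%. With the SD read as total, SE = SD x sqrt(1 - rho^2) x sqrt(1/12 + 1/36). Then SD 0.48 gives 92-94% (rho 0-0.3), inside the range, and SD 0.39 gives at least 98.6%, above it.

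**One pair of dose arms, 15 per arm.** SE = SD x sqrt(1 - rho^2) x sqrt(2/15) for total SD, or SD x sqrt(1 + ICC) x sqrt(2/15) for residual SD. Worked case, SD 0.39 and rho 0: SE = 0.39 x 0.3651 = 0.1424; power = Phi(0.27/0.1424 - 1.645) = Phi(0.25) = 0.60; so 40% of trials are non-significant.

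Both parts of hypothesis b are met when the observed difference D satisfies |D| <= c, where c is the smaller of the cut-off for small and 1.645 x SE. With a true difference of 0.27, that probability is Phi((c - 0.27)/SE) - Phi((-c - 0.27)/SE). Cut-offs of a quarter, a third and half of 0.54 are 0.135, 0.18 and 0.27.

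| SD, correlation | SE | Non-significant | Both, 0.135 | Both, 0.18 | Both, 0.27 | 90% CI half-width |
|---|---|---|---|---|---|---|
| total 0.39, 0 | 0.142 | 40% | 17% | 26% | 40% | 0.23 |
| total 0.39, 0.5 | 0.123 | 29% | 14% | 23% | 29% | 0.20 |
| total 0.48, 0 | 0.175 | 54% | 21% | 30% | 50% | 0.29 |
| total 0.48, 0.5 | 0.152 | 45% | 18% | 28% | 45% | 0.25 |
| total 0.39, 0.7 | 0.102 | 16% | 9% | 16% | 16% | 0.17 |
| total 0.48, 0.7 | 0.125 | 30% | 14% | 24% | 30% | 0.21 |
| residual 0.39, ICC 0.3 | 0.162 | 49% | 20% | 29% | 49% | 0.27 |
| residual 0.48, ICC 0.3 | 0.200 | 61% | 23% | 31% | 50% | 0.33 |

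**Smaller arms.** The CoASY analysis uses the Per-Protocol set, so arms may fall below 15. At 12 per arm and correlation 0, power for 0.27 is 40-52%, so 48-60% of trials are non-significant.

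**What a CI rule would deliver.** If two groups are truly equal, the 90% CI lies within +/-0.27 with probability 2 x Phi((0.27 - 1.645 x SE)/SE) - 1, or zero when the half-width exceeds 0.27. At correlation 0 and 0.5 this is 20% and 41% (SD 0.39), or 0% and 11% (SD 0.48). At correlation 0.7 it is 69% or 39%. At ICC 0.3 with residual SD it is 1% or 0%.

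**The case against.** The strongest reply is that the plan does not equate non-significance with equality. Hypothesis b also demands a small difference, and a strict reading of that part brings the error rate well below the non-significance rate. The sentence is a prediction in the design section, and hypothesis b does not appear among the secondary hypotheses in the synopsis or section 3. Elsewhere the plan gives effect sizes priority over power, and reads p-values below 0.1 together with the size and precision of the estimate. CoASY is an exploratory biomarker, the trial is not meant to find a dose, and the open-label dose is fixed in advance. The feedback-inhibition account also draws on the early rise, the later decline, the six-month dose pattern and the longitudinal model.

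Much of this stands, and it rules out three stronger readings that a reader might infer:

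- *The 29-54% is the rate of falsely declaring equality.* It is only the rate of non-significance; the second condition lowers the rate unless small is read as leniently as half the effect.
- *Hypothesis d also rests on a non-significant test.* It carries no such wording. It also compares initial groups that are by then all on one dose, so it is not a dose comparison.
- *The noisier the data, the easier the confirmation.* That is true of the non-rejection part alone. With small set at a quarter of 0.54 and truly equal doses, the chance of meeting both parts falls from 73% to 56% as the SE rises from 0.123 to 0.175. With a true 0.27 it rises only from 14% to 21%.

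The reply does not supply a cut-off, however. The size-and-precision rule governs when a result counts as significant, not when groups may be called alike, and hypothesis b is the only decision wording on dose equality in the documents.

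**Conclusion.** The concern holds as a gap in the decision rule for two secondary hypotheses. For b, non-rejection contributes little and the condition that could carry the conclusion has no number. Depending on whether small means a quarter, a third or half of 0.54, a true half-effect difference would satisfy the rule in about 14-21%, 23-30% or 29-50% of trials. For d, the criterion is missing. The dose-equality comparison is neither specified nor covered by the power statement.

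These figures rest on an undocumented correlation (0-0.5) with the SD read as total. Non-significance falls to 16-30% at correlation 0.7 and rises to 49-61% with residual SD and ICC 0.3. The effect and SD come from 8 classic PKAN children and 6 controls. The primary safety and tolerability aims are not affected.

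**What to change.** 1. For hypothesis b, remove non-rejection as a criterion.
2. For b and d, report each between-group difference with its 90% CI beside the active-minus-placebo change.
3. State in advance, as the sponsor's choice, the fraction of that change that counts as immaterial. Conclude no material difference only if the whole CI lies within it; otherwise report the comparison as inconclusive.
4. Describe the equality hypotheses as estimates, not confirmations.

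This changes SAP wording only. The cost is in what can be claimed: with a margin of +/-0.27, used here only as an illustration, truly equal groups would pass in about 0-41% of trials per pair (correlation 0-0.5), so most comparisons will probably be inconclusive. For 80% power to show equivalence at that margin, n per arm = 2 x (s x (1.645 + 1.282)/0.27)^2. That is about 36 (s = 0.39) or 55 (s = 0.48) at correlation 0, and about 47 or 71 with residual SD and ICC 0.3 (s = SD x sqrt(1.3)). The plan describes its sample size as limited by the rarity of the disease, so the realistic remedy is more modest wording rather than more participants.
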